## Phase 3 Study of Aducanumab in Early Alzheimer's Disease

Ab = antibody; AD = Alzheimer's disease; AE = adverse event; ADAS-Cog 13 = Alzheimer's Disease Assessment Scale Cognitive Subscale (13 items); ADCS-ADL-MCI = Alzheimer's Disease Cooperative Study-Activities of Daily Living Inventory (Mild Cognitive Impairment version); [REDACTED]; CDR = Clinical Dementia Rating; [REDACTED]; C-SSRS = Columbia Suicide Severity Rating Scale; ECG = electrocardiogram; [REDACTED]; EQ-5D (IR-S) = EQ-5D, informant reported on subject; LTE = long-term extension; MMSE = Mini-Mental State Examination; NPI-10 = Neuropsychiatric Inventory-10; PBMC = peripheral blood mononuclear cells; PET = positron emission tomography; [REDACTED]; SAE = serious adverse event; UV = unscheduled visit.

 Required for women of childbearing potential only (see Section 13.5).

 Sample will be collected prior to infusion (where applicable).

 Only for subjects who participate in the amyloid PET substudy. Amyloid PET may be scheduled within a window of  $\pm 7$  days.

CONFIDENTIAL

The information contained herein may not be used, disclosed, or published without the written consent of Biogen MA Inc.

**Table 5: Long-Term Extension Period Schedule From Week 136 to Week 182**

Study Week															UV for a Change in AD Medication
	136	140	144	148	152	156	160	162	164	168	172	176	180	182	
Study Day	953 ± 5	981 ± 5	1009 ± 5	1037 ± 5	1065 ± 5	1093 ± 5	1121 ± 5	1135 ± 5	1149 ± 5	1177 ± 5	1205 ± 5	1233 ± 5	1261 ± 5	1275 ± 5	
Body Weight	X	X	X	X	X	X	X		X	X	X	X	X	X	
Urine Pregnancy Test 	X	X	X	X	X	X	X		X	X	X	X	X	X	
Physical Examination					X							X		X	
Neurological Examination					X							X		X	
12-lead Paper ECG					X							X			
Vital Signs	X	X	X	X	X	X	X		X	X	X	X	X	X	
Hematology, Blood Chemistry and Urinalysis					X							X			
Anti-Aducanumab Ab 					X									X	
PBMC Collection					X									X	
Aducanumab Concentration 					X							X		X	
Study Drug Infusion	X	X	X	X	X	X	X		X	X	X	X	X		
Amyloid PET 														X	

CONFIDENTIAL

The information contained herein may not be used, disclosed, or published without the written consent of Biogen MA Inc.

Study Week															UV for a Change in AD Medication
	136	140	144	148	152	156	160	162	164	168	172	176	180	182	
Study Day	953 ± 5	981 ± 5	1009 ± 5	1037 ± 5	1065 ± 5	1093 ± 5	1121 ± 5	1135 ± 5	1149 ± 5	1177 ± 5	1205 ± 5	1233 ± 5	1261 ± 5	1275 ± 5	
CDR								X						X	X
MMSE								X						X	X
ADAS-Cog 13								X						X	X
ADCS-ADL-MCI								X						X	X
NPI-10								X						X	
EQ-5D (IR-S)								X						X	
C-SSRS								X						X	
AE Reporting	Monitor and record continuously throughout the study														
Concomitant Therapy and Procedures	Monitor and record continuously throughout the study														
SAE Reporting	Monitor and record continuously throughout the study														

Ab = antibody; AD = Alzheimer's disease; AE = adverse event; ADAS-Cog 13 = Alzheimer's Disease Assessment Scale-Cognitive Subscale (13 items); ADCS-ADL-MCI = Alzheimer's Disease Cooperative Study-Activities of Daily Living Inventory (Mild Cognitive Impairment version); [REDACTED]; CDR = Clinical Dementia Rating; [REDACTED]; C-SSRS = Columbia Suicide Severity Rating Scale; ECG = electrocardiogram; [REDACTED]; EQ-5D (IR-S) = EQ-5D, informant reported on subject; EOT = End of Treatment; FU = Follow-Up; LTE = long-term extension; MMSE = Mini-Mental State Examination; NPI-10 = Neuropsychiatric Inventory-10; PBMC = peripheral blood mononuclear cells; PET = positron emission tomography; [REDACTED]; SAE = serious adverse event; UV = unscheduled visit.

 Required for women of childbearing potential only (Section 15.5).

 Sample will be collected prior to infusion (where applicable).

[REDACTED]

 Only for subjects who participate in the amyloid PET substudy. Amyloid PET may be scheduled within a window of ±7 days.

CONFIDENTIAL

The information contained herein may not be used, disclosed, or published without the written consent of Biogen MA Inc.

CONFIDENTIAL

The information contained herein may not be used, disclosed, or published without the written consent of Biogen MA Inc.

**Table 6: Brain MRI, ARIA Management, and Follow-Up Phone Call Schedule From Weeks 80 to 182 of the Long-Term Extension Period**

Study Week	Long-Term Extension													Unscheduled Visit for ARIA 
	80	82	86	90	94	98	102	106	110	122	134	158	182	
Study Day	561 ± 5	575 ± 5	603 ± 5	631 ± 5	659 ± 5	687 ± 5	715 ± 5	743 ± 5	771 ± 5	855 ± 5	939 ± 5	1107 ± 5	1275 ± 5	
Follow-Up Phone Call 		X	X	X	X	X	X	X	X					
Brain MRI 					X		X		X	X	X	X	X	X 
Aducanumab Concentration 														X
MOCA	X													X
PBMC Collection 														X

ARIA = amyloid-related imaging abnormalities; ARIA-E = amyloid-related imaging abnormality-edema; ARIA-H = amyloid-related imaging abnormality-hemorrhage or superficial siderosis; EOT = End of Treatment; LTE = long-term extension; MOCA = Montreal Cognitive Assessment; MRI = magnetic resonance imaging; PBMC = peripheral blood mononuclear cells; PK = pharmacokinetic; [REDACTED]

 For the frequency of required brain MRI and MOCA assessments, and PK, biomarker, and PBMC sample collection for subjects who develop ARIA-E and/or ARIA-H, see Section 7.2.1.1 to Section 7.2.1.5. This includes PK, biomarker, and PBMC sample collection at the first unscheduled visit for ARIA monitoring per episode only. For the frequency of brain MRI and MOCA assessments following resolution of ARIA and resumption of dosing, see Section 7.2.1.6. For management of recurrent ARIA, see Section 7.2.1.7.

 Phone visit may be performed in person if the subject will be at the study site for clinical assessments.

 Arterial-spin labeling MRI and task-free functional MRI will be performed only at a subset of sites, and will not be performed at any visit after Week 182.

 One sample will be collected within ±2 days of the MRI visit. Exact collection date and time will be captured for all PK blood samples on a specified case report form.

 Sample may be collected within ±2 days of the MRI visit at the same time as sample collection for aducanumab concentration.

CONFIDENTIAL

The information contained herein may not be used, disclosed, or published without the written consent of Biogen MA Inc.

**Table 7: Long-Term Extension Period Schedule From Week 184 to Week 234**

Study Week														UV for ARIA 
	184	188	192	196	200	204	208	212	216	220	224	228	232	
Study Day	1289 ± 5	1317 ± 5	1345 ± 5	1373 ± 5	1401 ± 5	1429 ± 5	1457 ± 5	1485 ± 5	1513 ± 5	1541 ± 5	1569 ± 5	1597 ± 5	1625 ± 5	
Body Weight	X	X	X	X	X	X	X	X	X	X	X	X	X	
Urine Pregnancy Test 	X	X	X	X	X	X	X	X	X	X	X	X	X	
Physical Examination							X						X	
Neurological Examination							X						X	
Vital Signs	X	X	X	X	X	X	X	X	X	X	X	X	X	
Hematology, Blood Chemistry and Urinalysis													X	
PBMC Collection														X 
Aducanumab Concentration														X 
Study Treatment Infusion	X	X	X	X	X	X	X	X	X	X	X	X	X	
Brain MRI													X	X
CDR													X	
MMSE													X	
ADAS-Cog 13													X	
ADCS-ADL-MCI													X	
EQ-5D-(IR-5)													X	

CONFIDENTIAL

The information contained herein may not be used, disclosed, or published without the written consent of Biogen MA Inc.

Study Week														UV for ARIA 
	184	188	192	196	200	204	208	212	216	220	224	228	232	
Study Day	1289 ± 5	1317 ± 5	1345 ± 5	1373 ± 5	1401 ± 5	1429 ± 5	1457 ± 5	1485 ± 5	1513 ± 5	1541 ± 5	1569 ± 5	1597 ± 5	1625 ± 5	
MOCA														X
C-SSRS													X	
AE Reporting	Monitor and record continuously throughout the study													
Concomitant Therapy and Procedures	Monitor and record continuously throughout the study													
SAE Reporting	Monitor and record continuously throughout the study													

AD = Alzheimer's disease; AE = adverse event; ADAS-Cog 13 = Alzheimer's Disease Assessment Scale Cognitive Subscale (13 items); ADCS-ADL-MCI = Alzheimer's Disease Cooperative Study Activities of Daily Living Inventory (Mild Cognitive Impairment version); ARIA = amyloid-related imaging abnormalities; ARIA-E = amyloid-related imaging abnormality-edema; ARIA-H = amyloid-related imaging abnormality hemorrhage or superficial siderosis; CDR = Clinical Dementia Rating scale; C-SSRS = Columbia Suicide Severity Rating Scale; [REDACTED]; [REDACTED]; EQ-5D (IR-S) = EQ-5D, informant reported on subject; LTE = long-term extension; MMSE = Mini Mental State Examination; MOCA = Montreal Cognitive Assessment; MRI = magnetic resonance imaging; PBMC = peripheral blood mononuclear cells; PK = pharmacokinetic; [REDACTED]; SAE = serious adverse event; UV = unscheduled visit.

 For the frequency of required brain MRI and MOCA assessments, and PK, biomarker, and PBMC sample collection for subjects who develop ARIA-E and/or ARIA-H, see Section 7.2.1.1 to Section 7.2.1.5. This includes PK, biomarker, and PBMC sample collection at the first unscheduled visit for ARIA monitoring per episode only. For the frequency of brain MRI and MOCA assessments following resolution of ARIA and resumption of dosing, see Section 7.2.1.6. For management of recurrent ARIA, see Section 7.2.1.7.

 Required for women of childbearing potential only (Section 15.5).

 Sample may be collected within ±2 days of the MRI visit at the same time as sample collection for aducanumab concentration.

 One sample will be collected within ±2 days of the MRI visit. Exact collection date and time will be captured for all PK blood samples on a specified case report form.

CONFIDENTIAL

The information contained herein may not be used, disclosed, or published without the written consent of Biogen MA Inc.

**Table 8: Long-Term Extension Period Schedule From Week 236 to Week 286**

Study Week														UV for ARIA 
	236	240	244	248	252	256	260	264	268	272	276	280	284	
Study Day	1653 ± 5	1681 ± 5	1709 ± 5	1737 ± 5	1765 ± 5	1793 ± 5	1821 ± 5	1849 ± 5	1877 ± 5	1905 ± 5	1933 ± 5	1961 ± 5	1989 ± 5	
Body Weight	X	X	X	X	X	X	X	X	X	X	X	X	X	
Urine Pregnancy Test 	X	X	X	X	X	X	X	X	X	X	X	X	X	
Physical Examination							X						X	
Neurological Examination							X						X	
Vital Signs	X	X	X	X	X	X	X	X	X	X	X	X	X	
Hematology, Blood Chemistry and Urinalysis													X	
PBMC Collection														X 
Aducanumab Concentration														X 
Study Treatment Infusion	X	X	X	X	X	X	X	X	X	X	X	X	X	
Brain MRI													X	X
Amyloid PET 							X							
CDR													X	
MMSE													X	
ADAS-Cog 13													X	
ADCS-ADL-MCI													X	
EQ-5D-(TR-S)													X	

CONFIDENTIAL

The information contained herein may not be used, disclosed, or published without the written consent of Biogen MA Inc.

Study Week														
	236	240	244	248	252	256	260	264	268	272	276	280	284	UV for ARIA 
Study Day	1653 ± 5	1681 ± 5	1709 ± 5	1737 ± 5	1765 ± 5	1793 ± 5	1821 ± 5	1849 ± 5	1877 ± 5	1905 ± 5	1933 ± 5	1961 ± 5	1989 ± 5	
MOCA														X
C-SSRS													X	
AE Reporting	Monitor and record continuously throughout the study													
Concomitant Therapy and Procedures	Monitor and record continuously throughout the study													
SAE Reporting	Monitor and record continuously throughout the study													

AD = Alzheimer's disease; AE = adverse event; ADAS-Cog 13 = Alzheimer's Disease Assessment Scale Cognitive Subscale (13 items); ADCS-ADL-MCI = Alzheimer's Disease Cooperative Study Activities of Daily Living Inventory (Mild Cognitive Impairment version); ARIA = amyloid-related imaging abnormalities; ARIA-E = amyloid-related imaging abnormality-edema; ARIA-H = amyloid-related imaging abnormality hemorrhage or superficial siderosis; CDR = Clinical Dementia Rating scale; C-SSRS = Columbia Suicide Severity Rating Scale; [REDACTED] EQ-5D (IR-S) = EQ-5D, informant reported on subject; LTE = long-term extension; MMSE = Mini Mental State Examination; MOCA = Montreal Cognitive Assessment; MRI = magnetic resonance imaging; PBMC = peripheral blood mononuclear cells; PET = positron emission tomography; PK = pharmacokinetic; [REDACTED]; SAE = serious adverse event; UV = unscheduled visit.

 For the frequency of required brain MRI and MOCA assessments, and PK, biomarker, and PBMC sample collection for subjects who develop ARIA-E and/or ARIA-H, see Section 7.2.1.1 to Section 7.2.1.5. This includes PK, biomarker, and PBMC sample collection at the first unscheduled visit for ARIA monitoring per episode only. For the frequency of brain MRI and MOCA assessments following resolution of ARIA and resumption of dosing, see Section 7.2.1.6. For management of recurrent ARIA, see Section 7.2.1.7.

 Required for women of childbearing potential only (Section 15.5).

 Sample may be collected within ±2 days of the MRI visit at the same time as sample collection for aducanumab concentration.

 One sample will be collected within ±2 days of the MRI visit. Exact collection date and time will be captured for all PK blood samples on a specified case report form.

 Only for subjects who participate in the amyloid PET substudy. Amyloid PET may be scheduled within a window of ±7 days.

CONFIDENTIAL

The information contained herein may not be used, disclosed, or published without the written consent of Biogen MA Inc.

**Table 9: Long-Term Extension Period Schedule From Week 288 to the End of Treatment or Follow-Up**

Study Week																FU 
	288	292	296	300	304	308	312	316	320	324	328	332	336	338 EOT 	UV for ARIA 	354 (or 18 wks after final dose for subjects who DCT early)
Study Day	2017 ± 5	2045 ± 5	2073 ± 5	2101 ± 5	2129 ± 5	2157 ± 5	2185 ± 5	2213 ± 5	2241 ± 5	2269 ± 5	2297 ± 5	2325 ± 5	2353 ± 5	2367 ± 5		2479 ± 7
Body Weight	X	X	X	X	X	X	X	X	X	X	X	X	X	X		X
Urine Pregnancy Test 	X	X	X	X	X	X	X	X	X	X	X	X	X	X		X
Physical Examination							X							X		X
Neurological Examination							X							X		X
12-lead Paper ECG																X
Vital Signs	X	X	X	X	X	X	X	X	X	X	X	X	X	X		X
Hematology, Blood Chemistry and Urinalysis													X			X
Anti-Aducanumab Ab														X		X
PBMC Collection														X 	X 	X
Aducanumab Concentration														X	X 	X
Study Treatment Infusion	X	X	X	X	X	X	X	X	X	X	X	X	X			

CONFIDENTIAL

The information contained herein may not be used, disclosed, or published without the written consent of Biogen MA Inc.

Study Week																FU 	
	288	292	296	300	304	308	312	316	320	324	328	332	336	338 EOT 	UV for ARIA 	354 (or 18 who after final dose for subjects who DCT early)	
Study Day	2017 ± 5	2045 ± 5	2073 ± 5	2101 ± 5	2129 ± 5	2157 ± 5	2185 ± 5	2213 ± 5	2241 ± 5	2269 ± 5	2297 ± 5	2325 ± 5	2353 ± 5	2367 ± 5		2479 ± 7	
Brain MRI															X 	X	X 
Amyloid PET 															X		
CDR															X		X
MMSE															X		X
ADAS-Cog 13															X		X
ADCS-ADL-MCI															X		X
NPI-10															X 		
EQ-5D-(IR-5)															X		
MOCA																X	
C-SSRS															X		
AE Reporting	Monitor and record continuously throughout the study																
Concomitant Therapy and Procedures	Monitor and record continuously throughout the study																

CONFIDENTIAL

The information contained herein may not be used, disclosed, or published without the written consent of Biogen MA Inc.

Study Week															FU 	
	288	292	296	300	304	308	312	316	320	324	328	332	336	338 EOT 	UV for ARIA 	354 (or 18 wks after final dose for subjects who DCT early)
Study Day	2017 ± 5	2045 ± 5	2073 ± 5	2101 ± 5	2129 ± 5	2157 ± 5	2185 ± 5	2213 ± 5	2241 ± 5	2269 ± 5	2297 ± 5	2325 ± 5	2353 ± 5	2367 ± 5		2479 ± 7
SAE Reporting	Monitor and record continuously throughout the study.															

Ab = antibody; AD = Alzheimer's disease; AE = adverse event; ADAS-Cog 13 = Alzheimer's Disease Assessment Scale Cognitive Subscale (13 items); ADCS-ADL-MCI = Alzheimer's Disease Cooperative Study Activities of Daily Living Inventory (Mild Cognitive Impairment version); ARIA = amyloid-related imaging abnormalities; ARIA-E = amyloid-related imaging abnormality-edema; ARIA-H = amyloid-related imaging abnormality hemorrhage or superficial siderosis; [REDACTED]; CDR = Clinical Dementia Rating scale; [REDACTED]; C-SSRS = Columbia Suicide Severity Rating Scale; DCT = discontinue treatment; ECG = electrocardiogram; EOT = end of treatment; [REDACTED]; EQ-5D (IR-S) = EQ-5D, informant reported on subject; FU = follow-up; LTE = long-term extension; MMSE = Mini Mental State Examination; MOCA = Montreal Cognitive Assessment; MRI = magnetic resonance imaging; NPI-10 = Neuropsychiatric Inventory-10; PBMC = peripheral blood mononuclear cells; PET = positron emission tomography; PK = pharmacokinetic; [REDACTED]; SAE = serious adverse event; UV = unscheduled visit; wks = weeks.

 Subjects who complete the LTE period are to return to the site for a safety FU Visit at Week 354. Subjects who discontinue treatment or withdraw from the study early are to have a safety FU Visit at 18 weeks after their final dose.

 Subjects who discontinue treatment prematurely are to remain in the study, attend a FU Visit 18 weeks after the final dose, and immediately continue protocol-required tests and assessments continue protocol-required tests and assessments at a subset of the clinic visits (see Table 11) until the end of the study per the schedule of events. (It is possible that a clinic visit will occur before the FU Visit.) If the FU Visit will occur within 2 weeks of a scheduled clinic visit, then the FU Visit can be combined with the scheduled visit and all assessments required for both visits performed at this single visit. Subjects who withdraw from study prematurely are to return to the site for an EOT Visit. For subjects who discontinue treatment early, efficacy assessments specified at the EOT visit are not required if the subject discontinues treatment within 3 months of the previous efficacy assessment visit and no significant changes in cognitive status are suspected by the Investigator. The site should notify the Sponsor in such cases.

 For the frequency of required brain MRI and MOCA assessments, and PK, biomarker, and PBMC sample collection for subjects who develop ARIA-E and/or ARIA-H, see Section 7.2.1.1 to Section 7.2.1.5. This includes PK, biomarker, and PBMC sample collection at the first unscheduled visit for ARIA monitoring per episode only. For the frequency of brain MRI and MOCA assessments following resolution of ARIA and resumption of dosing, see Section 7.2.1.6. For management of recurrent ARIA, see Section 7.2.1.7.

 Required for women of childbearing potential only (see Section 15.5).

 This assessment is only to be performed if the EOT Visit is at or before Week 182.

 Sample may be collected within ±2 days of the MRI visit at the same time as sample collection for aducanumab concentration.

CONFIDENTIAL

The information contained herein may not be used, disclosed, or published without the written consent of Biogen MA Inc.

 One sample will be collected within  $\pm 2$  days of the MRI visit. Exact collection date and time will be captured for all PK blood samples on a specified case report form.

 Arterial-spin labeling MRI and task-free functional MRI will be performed only at a subset of sites, and will not be performed at any visit after Week 182.

 Only for subjects who participate in the amyloid PET substudy. Amyloid PET may be scheduled within a window of  $\pm 7$  days.

CONFIDENTIAL

The information contained herein may not be used, disclosed, or published without the written consent of Biogen MA Inc.

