-  Subjects who withdraw from study prematurely are to return to the site for an EOT Visit; for such subjects, efficacy assessments specified at the EOT Visit are not required if the subject discontinues treatment within 3 months of the previous efficacy assessment visit and no significant changes in cognitive status are suspected by the Investigator. The site should notify the Sponsor in such cases.
-  For the frequency of required brain MRI and MOCA assessments, and PK, biomarker, and PBMC sample collection for subjects who develop ARIA-E and/or ARIA-H, see Section 7.2.1.1 to Section 7.2.1.5. This includes PK, biomarker, and PBMC sample collection at the first unscheduled visit for ARIA monitoring per episode only. For the frequency of brain MRI and MOCA assessments following resolution of ARIA and resumption of dosing, see Section 7.2.1.6. For management of recurrent ARIA, see Section 7.2.1.7.
-  Only for subjects entering the long-term extension period.
-  Sample may be collected within  $\pm 2$  days of the MRI visit at the same time as sample collection for aducanumab concentration.
-  One sample will be collected within  $\pm 2$  days of the MRI visit. Exact collection date and time will be captured for all PK blood samples on a specified case report form.
-  Arterial spin labeling MRI and task-free functional MRI will be performed only at a subset of sites.
-  Only for subjects who participate in the amyloid PET substudy. Amyloid PET may be scheduled within a window of  $\pm 7$  days.

CONFIDENTIAL

The information contained herein may not be used, disclosed, or published without the written consent of Biogen MA Inc.

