**Table 11: Subjects Who Discontinue Study Treatment but Remain in the Study – Long-Term Extension Period**

Study Week	LTE Period 															UV for ARIA 
	92	104	106	128	134	152	162	176	182	208	232	260	284	312	338 (EOT) 	
Study Day	645 ± 5	729 ± 5	743 ± 5	897 ± 5	939 ± 5	1065 ± 5	1135 ± 5	1233 ± 5	1275 ± 5	1457 ± 5	1625 ± 5	1821 ± 5	1989 ± 5	2185 ± 5	2367 ± 5	
Body Weight	X	X		X		X		X	X	X	X	X	X	X	X	
Physical Examination	X	X		X		X		X	X	X	X	X	X	X	X	
Neurological Examination	X	X		X		X		X	X	X	X	X	X	X	X	
12-lead Paper ECG		X		X		X		X								
Vital Signs	X	X		X		X		X	X	X	X	X	X	X	X	
Hematology, Blood Chemistry and Urinalysis		X		X		X		X			X		X			
PBMC Collection																X 
Aducanumab Concentration																X 
Brain MRI 					X				X		X		X		X 	X
Amyloid PET 									X			X			X	
CDR			X		X		X		X		X		X		X	
MMSE			X		X		X		X		X		X		X	
ADAS-Cog 13			X		X		X		X		X		X		X	
ADCS-ADL-MCI			X		X		X		X		X		X		X	
NPI-10			X		X		X		X						X 	

CONFIDENTIAL

The information contained herein may not be used, disclosed, or published without the written consent of Biogen MA Inc.

Study Week	LTE Period 															UV for ARIA 
	92	104	106	128	134	152	162	176	182	208	232	260	284	312	338 (EOT) 	
Study Day	645 ± 5	729 ± 5	743 ± 5	897 ± 5	939 ± 5	1065 ± 5	1135 ± 5	1233 ± 5	1275 ± 5	1457 ± 5	1625 ± 5	1821 ± 5	1989 ± 5	2185 ± 5	2367 ± 5	
EQ-5D-(IR-S)			X		X		X		X		X		X		X	
MOCA																X
C-SSRS			X		X		X		X		X		X		X	
AE Reporting	Monitor and record continuously throughout the study															
Concomitant Therapy and Procedures	Monitor and record continuously throughout the study															
SAE Reporting	Monitor and record continuously throughout the study															

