AD = Alzheimer's disease; AE = adverse event; ADAS-Cog 13 = Alzheimer's Disease Assessment Scale Cognitive Subscale (13 items); ADCS-ADL-MCI = Alzheimer's Disease Cooperative Study Activities of Daily Living Inventory (Mild Cognitive Impairment version); ARIA = amyloid-related imaging abnormalities; ARIA-E = amyloid-related imaging abnormality-edema; ARIA-H = amyloid-related imaging abnormality hemorrhage or superficial siderosis; [REDACTED]; CDR = Clinical Dementia Rating scale; [REDACTED]; C-SSRS = Columbia Suicide Severity Rating Scale; ECG = electrocardiogram; EOT = end of treatment; [REDACTED]; EQ-5D (IR-S) = EQ-5D, informant reported on subject; FU = follow-up; LTE = long-term extension; MMSE = Mini Mental State Examination; MOCA = Montreal Cognitive Assessment; MRI = magnetic resonance imaging; NPI 10 = Neuropsychiatric Inventory-10; PBMC = peripheral blood mononuclear cells; PET = positron emission tomography; PK = pharmacokinetic; [REDACTED]; SAE = serious adverse event; UV = unscheduled visit.

-  Subjects who discontinue study treatment during the LTE period are to remain in the study, attend a FU Visit as listed in Table 9, and then will continue protocol-required tests and assessments at a subset of the clinic visits.
-  Subjects who withdraw from study prematurely are to return to the site for an EOT Visit; for such subjects, efficacy assessments specified at the EOT Visit are not required if the subject discontinues treatment within 3 months of the previous efficacy assessment visit and no significant changes in cognitive status are suspected by the Investigator. The site should notify the Sponsor in such cases.
-  For the frequency of required brain MRI and MOCA assessments, and PK, biomarker, and PBMC sample collection for subjects who develop ARIA-E and/or ARIA-H, see Section 7.2.1.1 to Section 7.2.1.5. This includes PK, biomarker, and PBMC sample collection at the first unscheduled visit for ARIA monitoring per episode only. For the frequency of brain MRI and MOCA assessments following resolution of ARIA and resumption of dosing, see Section 7.2.1.6. For management of recurrent ARIA, see Section 7.2.1.7.
-  This assessment is only to be performed if the EOT Visit is at or before Week 182.
-  Sample may be collected within ±2 days of the MRI visit at the same time as sample collection for aducanumab concentration.

CONFIDENTIAL

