## 10. DISCONTINUATION OF STUDY TREATMENT AND/OR WITHDRAWAL OF SUBJECTS FROM THE STUDY

### 10.1. Discontinuation of Study Treatment

A subject *must* permanently discontinue study treatment for any of the following reasons:

- The subject develops any of the following:
  - ARIA-E accompanied by serious clinical symptoms except for “other medically important event” as defined in [Table 13](#).
  - Symptomatic ARIA-H (microhemorrhages) with serious clinical symptoms except for “other medically important event” as defined in [Table 14](#).
  - Symptomatic ARIA-H (superficial siderosis) with or serious clinical symptoms except for “other medically important event” as defined in [Table 15](#).
  - ARIA-H with  $\geq 10$  microhemorrhages and/or  $>2$  focal areas of superficial siderosis.
  - Any new incident macrohemorrhage (defined as  $>1$  cm in diameter on T2\* sequence).

See Section 7.2.1 for full details regarding discontinuation and dose reduction due to ARIA-E or ARIA-H.

- The subject becomes pregnant. Study treatment must be discontinued immediately and pregnancy must be reported according to the instructions in Section 15.4.1.
- The subject withdraws consent to continue study treatment.
- The subject experiences a medical emergency that necessitates permanent discontinuation of study treatment or unblinding of the subject's treatment assignment.
- The subject experiences an AE that does not resolve or requires continued treatment that meets exclusionary criteria (see Section 11.5.1.2).
- The subject experiences a severe infusion reaction.
- At the discretion of the Investigator for medical reasons.
- At the discretion of the Investigator or Sponsor for noncompliance.

The reason for discontinuation of study treatment must be recorded in the subject's case report form (CRF).

A subject who discontinues treatment is to remain in the study, attend a FU Visit 18 weeks after the final dose, and immediately continue protocol-required tests and assessments at a subset of the clinic visits (see [Table 10](#) and [Table 11](#)) until the end of the study per the schedule of events or until the subject withdraws consent.

CONFIDENTIAL

The information contained herein may not be used, disclosed, or published without the written consent of  
Biogen MA Inc.

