## 10.2. Withdrawal of Subjects From Study

Subjects must be withdrawn from the study for any one of the following reasons:

- The subject withdraws consent.
- The subject is unwilling or unable to comply with the protocol.
- At the discretion of the Investigator or Sponsor.

Note: A subject who discontinues study treatment will not be automatically withdrawn from the study, regardless of the number of doses missed. The subject is to remain in the study, and continue with a FU Visit 18 weeks after the final dose, and protocol-required tests and assessments at a subset of the clinic visits (see [Table 10](#) and [Table 11](#)) until the end of the study or until the subject withdraws consent.

The reason for the subject's withdrawal from the study must be recorded in the subject's CRF.

Subjects who are withdrawn from the study after receiving  $\geq 1$  doses of study treatment should complete the EOT Visit after the reason for withdrawal is identified. For such subjects, efficacy assessments specified at the EOT Visit are not required if the subject discontinues treatment within 3 months of the previous efficacy assessment visit and no significant changes in cognitive status are suspected by the Investigator; The site should notify the sponsor in such cases. Subjects who are withdrawn from the study are also to return to the site for a FU Visit 18 weeks after receiving their last dose of study treatment.

CONFIDENTIAL

The information contained herein may not be used, disclosed, or published without the written consent of  
Biogen MA Inc.

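### Table 9 footnote 2 lets sites omit end-of-treatment efficacy scales that Table 11 requires for the same subjects, and every copy of the waiver is timed from stopping treatment rather than leaving the study

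*Protocol*

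**What the plan says.** All references are to protocol version 6.0.

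- **Table 9, footnote 2** first places treatment discontinuers in continued follow-up: "Subjects who discontinue treatment prematurely are to remain in the study, attend a FU Visit 18 weeks after the final dose", with further assessments on the Table 11 schedule. It then says that study withdrawers return for an EOT Visit. A new sentence gives the waiver: "For subjects who discontinue treatment early, efficacy assessments specified at the EOT visit are not required if the subject discontinues treatment within 3 months". That interval is counted from the preceding efficacy visit. The waiver has a second condition: "no significant changes in cognitive status are suspected by the Investigator".
- **Table 11** is headed "Subjects Who Discontinue Study Treatment but Remain in the Study" and covers the extension. Its Week 338 (EOT) column is marked for CDR, MMSE, ADAS-Cog 13 and ADCS-ADL-MCI. Its footnote 2 gives the waiver to a different group: "Subjects who withdraw from study prematurely are to return to the site for an EOT Visit; for such subjects, efficacy assessments".
- **Table 2 footnote 2, Table 3 footnote 3 and Table 10 footnote 2** also tie the waiver to study withdrawal. Section 10.2 does the same, opening with "Subjects who are withdrawn from the study after receiving".
- **Section 10.1** confirms that stopping treatment is not leaving: "A subject who discontinues treatment is to remain in the study, attend a FU Visit 18 weeks after" the final dose.
- **Sections 7.3.3 and 7.5** put the EOT Visit of a subject who continues in the extension at Week 338, or when the last subject has had the Week 182 Visit, whichever is first.

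**The concern.** There are two separate faults.

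The first is a contradiction about who is covered. A site that follows Table 9 may omit the four scales at EOT for a subject who stopped treatment and stayed. A site that follows Table 11 must do them.

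The second is the clock. A waiver of this kind makes sense if it skips a retest shortly after the last one. Here the 3 months run between the previous efficacy visit and the treatment stop. For a subject who stopped some time ago, that interval says nothing about the age of the last score on the day of withdrawal or EOT. This wording is in every copy of the waiver; Table 10, for example, has "efficacy assessments specified at the EOT Visit are not required if the subject discontinues treatment within 3 months of the previous efficacy assessment visit".

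At stake are late scores in subjects off treatment, whom the protocol goes out of its way to keep under observation. Any scores omitted would belong to those whom the Investigator considers stable, so the gaps would not be random. EOT data would also lean towards subjects still on drug.

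**Working it through.** **Who is covered**

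| Place | Waiver applies to |
|---|---|
| Table 2 fn 2, Table 3 fn 3 | study withdrawers |
| Table 10 fn 2, Table 11 fn 2 | study withdrawers |
| Section 10.2 | subjects withdrawn from the study |
| Table 9 fn 2 | subjects who stop treatment early |

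Table 9 is the only outlier, and the subjects it names are those whom Table 11 schedules for the scales at EOT.

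**What the clock measures**

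Inputs from the schedules:
- Efficacy visits for subjects off treatment in the placebo-controlled period: Weeks 26, 50 and 78 (Table 10).
- Efficacy visits for subjects off treatment in the extension: Weeks 106, 134, 162, 182, 232, 284 and 338 (Table 11).
- The FU Visit 18 weeks after the final dose also carries all four scales (FU columns of Tables 2 and 9), so it must be counted.
- 3 months is taken as 13 weeks, and the last dose as the date of stopping. The previous efficacy visit is read as the one before the stop.

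Formulas: time condition = stop week − previous efficacy week ≤ 13. Age of last score = exit week − most recent efficacy week, FU Visit included.

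*Extension, subject who stays (Table 9 wording).* Last dose Week 244.
- Time condition: 244 − 232 = 12 weeks, met.
- FU Visit: 244 + 18 = Week 262. Next Table 11 scales: Week 284. EOT: Week 338.
- Age of last score at EOT: 338 − 284 = **54 weeks**.

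*Placebo-controlled period, subject who later withdraws (Table 10 and Section 10.2 wording).* Last dose Week 28, withdrawal Week 77.
- Time condition: 28 − 26 = 2 weeks, met.
- FU Visit: 28 + 18 = Week 46. Table 10 scales: Week 50.
- Age of last score at withdrawal: 77 − 50 = **27 weeks**.

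**How often the time condition is met, by schedule**

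Extension doses run every 4 weeks from Week 80 to Week 336: (336 − 80)/4 + 1 = 65 doses. Doses no more than 13 weeks after the last scheduled efficacy visit:

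| Efficacy visit | Dose weeks | Count |
|---|---|---|
| 78 | 80, 84, 88 | 3 |
| 106 | 108, 112, 116 | 3 |
| 134 | 136, 140, 144 | 3 |
| 162 | 164, 168, 172 | 3 |
| 182 | 184, 188, 192 | 3 |
| 232 | 232, 236, 240, 244 | 4 |
| 284 | 284, 288, 292, 296 | 4 |

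The total is 23, and 23/65 = 35%. The count is the same with 12 weeks.

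**The case against.** The Table 9 sentence directly follows one about study withdrawers and is probably a drafting slip. Table 11 is the dedicated schedule for subjects who stay, and most sites would follow it. The waiver needs both conditions, and it permits omission without forbidding the assessment. Only the EOT score is in play: the earlier Table 11 visits and the FU Visit still carry the scales. All of this stands. It limits the consequence but does not remove the contradiction.

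It could also be said that EOT in Table 9 means a visit held when treatment stops. Sections 7.3.3 and 7.5 do not support that for subjects who continue in the study.

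A reader might infer more than the documents support, in three ways.
- *No score after stopping.* One could take the scale before the treatment stop as the last one available. The FU Visit adds a scheduled set 18 weeks after the final dose, which makes many gaps much shorter. For example, a last dose at Week 28 with withdrawal at Week 49 leaves a score 49 − 46 = 3 weeks old.
- *Damage to the primary endpoint.* The Table 9 conflict does not reach Week 78. Table 10 keeps the scales at Week 78 for subjects who stay, and the placebo-controlled copies of the waiver cover only withdrawers.
- *A third of stoppers lose their EOT score.* The 35% is a share of dose dates meeting one of two conditions. It predicts no number of missing scores.

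**Conclusion.** The contradiction is real and lies within current text. Table 9 footnote 2 permits omission of EOT scales that Table 11 requires for the same subjects, against five other places that restrict the waiver to study withdrawers. It affects the EOT score for the tertiary extension endpoints (Section 6.5.2).

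The timing fault is also real and is common to all copies. The condition can be met when the last score is 54 weeks old at EOT or 27 weeks old at withdrawal, well beyond 3 months in both cases.

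These ages assume that the FU Visit and every scheduled visit are attended. The 54 weeks further assumes that EOT falls at Week 338 and not at the earlier study-wide trigger. Both also assume that the previous visit is the one before the treatment stop. If it is read as the latest visit before exit, the two examples fail the condition (284 − 244 = 40 weeks; 50 − 28 = 22 weeks). On that reading the phrase still measures distance from the treatment stop, not from exit.

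How many scores would be lost cannot be estimated from the protocol. This is a small point, worth correcting because it is specific and nearly free.

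**What to change.** 1. In Table 9 footnote 2, restrict the waiver to subjects who withdraw from the study, as Table 11 footnote 2 and Section 10.2 do. Table 11's EOT scales then apply to everyone who stays.
2. In every copy of the waiver, make study withdrawal the timed event. The condition would read: *withdraws from the study within 3 months of the most recent efficacy assessment*. The copies are Table 2 footnote 2, Table 3 footnote 3, footnote 2 of Tables 9, 10 and 11, and Section 10.2. Changing only some of them would create a new inconsistency. Using the most recent assessment also lets the FU Visit count and settles which visit is meant.

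The cost is a wording change and a few more exit assessments at visits already scheduled.
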